During the home visit or telehealth visits that follows, the CHW will provide a timer, a fitness tracker bracelet to measure steps, an elastic resistance band, and an exercise diary. They may also provide the patient with a ergo cycle to enable them to conduct the aerobic exercises sitting down if walking is too burdensome or the patient is considered to be at high fall risk. The CHW and patient will consider the space available for exercise, such as a hallway, common space in the building (e.g., lobby, gathering room, etc.), outdoors during favorable weather, and local facilities like senior centers or churches. Once the area for exercise is selected, the CHW will demonstrate or explain the walking and resistance training routines and observe the patient perform them on his/her own. The two will set a schedule for exercising and post the schedule and instructions prominently in the home.

	Protocol Name:	Comprehensive Home-based Self-management Support for COPD Patients
	Principal Investigator:	[name], MPH
	Primary Contact Name/Contact Info:	[name]; [contact]; [contact]
	Date Revised:	4/16/21
	Study Number:	STUDY-18-01345

If the patient is unable to ambulate, or their gait appears unstable, they will be provided with a hand pedal ergometer, which they will use in place of walking for exercise. They will be allowed to keep the ergometer at completion of the study.

Resistance training will consist of a simple routine of upper and lower extremity extension and abduction movements with the elastic band. Each movement will be performed for 8-12 repetitions. The walking routine will last 20-40 minutes and the patient's pace will be guided by an audible click from the timer that is set by the CHW. The patient will be asked to perform the complete exercise routine 5 days a week. The CHW will directly supervise the patient in person or over the phone multiple times over the 6-month intervention period. She will call periodically to support the patient when she is unable to visit.

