b. Community Health Workers: CHWs are a part of the study team and will be assessed for internal quality assurance purposes only. Currently there is not a clear intent to contribute to generalizable knowledge with this data. If the data are re-examined or re-analyzed and new information surfaces that would contribute to generalizable knowledge, an application will be submitted to the IRB. Their performance is being evaluated for internal quality assurance for this study.

c. Recruitment and Interviewing. We will identify potentially eligible patients through queries of the Epic clinical record. RAs will obtain permission from the physician to recruit their patient then send a letter to the patient describing the study. One week later, the RA will phone the patient to answer questions and check eligibility of the participant. Eligible patients will be scheduled for an in-person baseline interview and enrolled in the study. Baseline interviews will occur at a location/time of the patient's choosing. RAs will reschedule missed interview appointments up to three times, after which patients will be considered dropouts. RAs blinded to treatment allocation will interview patients at 6 and 9 months.

d. Video Conferencing. Some visits with the community health worker may take place over Zoom conferencing or VSee video call, the Icahn School of Medicine approved HIPAA compliant version. Both Zoom and VSee ensure HIPAA compliance by preventing the sharing and collection of PHI and by encrypting audio and video data (for more information: <https://zoom.us/docs/doc/Zoom-hipaa.pdf>; <https://vsee.com/hipaa>).

Enrolled participants will be contacted via phone or email, based on their preferred method of contact, and provided with a link and password to access a Zoom session. A trained member of the research staff will meet with the participant over Zoom at the scheduled time to complete the visit. As an alternative method, participants will be sent a text or email with a link to open up a VSee video call.

If participant responses during the visit raise any concerns about patient safety, the research staff member will follow a modified version of the study protocol for risk assessment. The modification will be as follows:

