Primary Outcomes: COPD symptoms, inhaler technique, and exercise activity. COPD symptoms will be measured with the 8-item COPD Assessment Test (CAT) (score range 0-40), the 14-item Chronic Respiratory disease Questionnaire (CRQ), and the Medical Research Council Scale. Inhaler technique: We will assess proficiency in use of MDI and DPI placebo devices (Spirit Medical Devices, Murrysville, PA) and medication tracking devices (Propeller Health, Madison Wisconsin) using validated checklists and adapt these checklists for technique assessment with users of Elipta and Respimat inhalers. The Propeller Health devices can aid patients in medication adherence and understanding of their triggers for COPD and asthma. Exercise in the past 7 days will be measured with the 13-item Physical Activity Adult Questionnaire (PAAQ) and a wearable activity monitor, the Actigraph, which will be worn for 1 week intervals at baseline, 6 and 9 months. Secondary Outcomes. Self-reported medication adherence will be measured with the self-reported Medication Adherence Reporting Scale (MARS)., and with an electronic monitoring device that is attached to the inhaler. Exercise tolerance will be measured at baseline, 6- and 9-months using the 6- minute walk test (6MWT). We will ask about use of an action plan for COPD exacerbation.

h. Fidelity. Fidelity will be assessed through abstraction of CHWs' documentation in Community Health Works' documentation, direct observation of the CHWs, and qualitative exit interviews with patients and CHWs. The project manager will conduct unannounced

	Protocol Name:	Comprehensive Home-based Self-management Support for COPD Patients
	Principal Investigator:	[name], MPH
	Primary Contact Name/Contact Info:	[name]; [contact]; [contact]
	Date Revised:	4/16/21
	Study Number:	STUDY-18-01345

observations of each CHW monthly during the trial. She will also audio/video tape these encounters to review with the CHW for skills development.

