i. **Qualitative Data Collection and Analysis.** We will conduct semi-structured exit interviews with patients and CHWs to assess feasibility and perceptions of SaMBA-COPD to guide refinement. Interviews will follow the month 9 interview or at study dropout (30-45 minutes; compensation, \$20). Topics will include satisfaction, burden (physical, emotional, social), convenience, perceived positive or negative effects, and appropriateness. At trial completion, we will conduct qualitative interviews with CHWs and their supervisor and PR staff and physicians to assess the same topics. All interviews will be audio/video-recorded. These interviews will be used for internal evaluation and quality improvement.

j **Quantitative Data Analysis.**

Primary analyses. We will analyze outcomes on the intention-to-treat principle. The primary outcomes are CAT score, ICS technique, and PAAQ scores at 9 months.

Description of Data that Will Be Collected Including Long-Term Follow-Up

Disease beliefs: will be measured with the brief Illness Perceptions Questionnaire (IPQ; available in English and Spanish) that includes items for each of the 5 cognitive domains of the SRM.(15) Medications Beliefs: We will use the Beliefs about Medicines Questionnaire, an English and Spanish validated 10-item scale that measures beliefs about controller medication in 2 subdomains: necessity and concerns (reliability: 0.80). (16) Items will be added to assess expectations of benefits and emotional representations about medications (worried about side effects or addiction, upset about medication regimen, etc.).

Adherence: COPD controller medication adherence, electronically measured: Objective measurement using the Smartinhaler electronic device for metered dose inhalers (MDIs) and the Smartdisk for dry powder inhalers (DPIs) for 4 weeks after each research interview. RAs will attach the monitoring device to the inhaler, and patients will return them in a pre-stamped envelope. Adherence will be defined as use of medications on #70% of days prescribed, a commonly applied convention.

Cognitive: Quick mild cognitive impairment screen (QMCI).

Lifestyle: physical activity, electronically measured: objective measurement using Actigraph. Physical activity adult questionnaire (PAAQ). Smoking/alcohol/drug activity. Activities of daily living questionnaire (ADL), general health (single item). Comorbidities (Charlson Index).

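### The protocol lists both the PAAQ and the Actigraph as primary activity measures but analyses only the self-reported PAAQ as primary, so differential reporting between arms could pass for benefit

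*Protocol*

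**What the plan says.** The two statements of the primary outcomes, both in Protocol section 3(e), do not match.

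- Item g (Quantitative Data Collection) sets the domains: "Primary Outcomes: COPD symptoms, inhaler technique, and exercise activity". For the third domain it gives two instruments: "Exercise in the past 7 days will be measured with the 13-item Physical Activity Adult Questionnaire (PAAQ) and a wearable activity monitor, the Actigraph", the latter "which will be worn for 1 week intervals at baseline, 6 and 9 months". The secondary outcomes begin only after this.
- Item j (Quantitative Data Analysis), under primary analyses, gives the list to be analysed: "The primary outcomes are CAT score, ICS technique, and PAAQ scores at 9 months". The Actigraph is not in it.
- The description of data to be collected, directly after item j, characterises the device: "physical activity, electronically measured: objective measurement using Actigraph".

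The SAP names no primary outcome and mentions neither instrument. It applies P<0.05 to all outcome analyses and says that the trial was not powered.

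On blinding, item c says: "RAs blinded to treatment allocation will interview patients at 6 and 9 months". No blinding of patients is described. On exercise, Step 6 gives patients in the home-based exercise programme (HBEP) a step tracker, an exercise diary and a schedule displayed in the home, and sets a target: "The patient will be asked to perform the complete exercise routine 5 days a week". HBEP is entered only if the patient expresses interest. The control arm (item f) is three community health worker visits built around an education booklet, with no exercise target or diary described.

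**The concern.** The PAAQ asks patients how much they exercised in the past week. One arm contains patients who were given a weekly exercise target and asked to record their sessions; the other does not. Blinding the interviewer does not change what the patient knows or would like to report, and the two arms differ too visibly for patients to be unaware of what they received. A higher PAAQ score in the intervention arm could therefore reflect sharper recall or a wish to please, with no change in activity.

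An accelerometer worn at the same three time points is much less exposed to this, and the protocol itself calls it objective. If the analysis sentence governs, the activity conclusion rests on the more vulnerable measure alone. If the data-collection item governs, there are two primary activity measures and no rule for what to conclude when they disagree. Either way, a misleading activity signal could be carried into the design of a later, larger trial.

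**Working it through.** **Inputs from the documents.** 58 patients randomised, so 58/2 = 29 per arm. Significance level 0.05 (SAP); sidedness is not stated, and two-sided is assumed. Neither document gives an SD, effect size, dropout rate, HBEP uptake or power figure, so there is no stated figure to reproduce.

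**Assumption.** There is no true effect on activity, but average PAAQ reporting in the intervention arm is shifted upward by d standard deviations relative to control. The documents do not give d, so a range is shown.

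**Formula.** Two-sample t test with n = 29 per arm: df = 2 × 29 − 2 = 56, critical value 2.003, non-centrality = d × √(29/2) = 3.808 × d. The chance of P<0.05 is the probability that a non-central t falls outside ±2.003.

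| Arm-level shift d | Non-centrality | P<0.05, either direction | P<0.05, favouring intervention |
|---|---|---|---|
| 0 | 0 | 5.0% | 2.5% |
| 0.1 | 0.381 | 6.6% | 5.6% |
| 0.2 | 0.762 | 11.6% | 11.3% |
| 0.3 | 1.142 | 20.2% | 20.1% |
| 0.5 | 1.904 | 46.5% | 46.5% |

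**Dilution by opt-in.** Under intention to treat, arm-level shift = HBEP uptake × shift among those coached. At an assumed 50% uptake, shifts of 0.2, 0.3 and 0.5 SD among the coached become 0.10, 0.15 and 0.25 SD in the arm. The chance of P<0.05 is then 6.6%, 8.7% and 15.5%.

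**Dropout.** At an assumed 20% loss (29 × 0.8 ≈ 23 per arm), arm-level shifts of 0.2, 0.3 and 0.5 SD give 10.2%, 16.9% and 38.2%.

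**Effect of the planned model.** The SAP uses a difference-in-differences approach. A reporting shift that arises in one arm after randomisation is not removed by subtracting baseline. With equal variances and baseline correlation r, the SD of a change score is SD × √(2(1 − r)). At r = 0.5 this equals SD and the table is unchanged; at higher r the same shift is more likely to reach significance, and at lower r less likely. The documents do not give r.

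**The case against.** Several points on the other side are sound.

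- *The Actigraph is already listed as primary.* A reader who sees only the analysis sentence might infer that the sponsor chose to exclude the objective measure. The documents do not support that: the data-collection item puts it under the primary heading. What they show is an unreconciled inconsistency.
- *Not every intervention patient is coached to exercise.* A reader might infer that the whole arm receives the target and diary. HBEP is opt-in, so any shift from it is diluted.
- *There are safeguards.* Interviewers are blinded, controls also receive visits, and the intervention ends at month 6 while the endpoint asks about one week at month 9. These lessen the bias. None reaches a patient's knowledge of what they were taught to do.
- *The Actigraph is not neutral between arms.* A tempting conclusion is that it should replace the PAAQ as sole primary. Step 6 includes resistance bands, a cycle and a hand-pedal ergometer, which an activity monitor is likely to record poorly; that could hide real activity mainly in the intervention arm. HBEP patients also receive a step tracker, so wearing behaviour could differ by arm. The documents do not justify sole-primary status.
- *CAT is self-reported too.* True, but the plan lists no objective measure of symptoms as primary. For activity it lists one and then omits it.
- *This is an unpowered feasibility trial, and nothing says a benefit will be claimed on the PAAQ alone.* This limits the consequence. The SAP still tests every outcome at P<0.05, and nothing in either document prevents such a claim.

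**Conclusion.** The concern holds as an inconsistency with a consequence. One part of the protocol makes both activity measures primary, another analyses only the self-reported one as primary, and the SAP does not settle it. That leaves an activity claim open to differential reporting.

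If the arm-level over-report were 0.1 to 0.5 SD with no true effect, P<0.05 would occur in about 7% to 46% of trials instead of 5%. These figures assume 29 per arm, a two-sided t test, no dropout and a shift whose size is not in the documents. Because HBEP is opt-in and coaching has stopped by month 9, the lower end is more plausible; the 46% should not be read as an estimate of this trial's error rate. That patients know their arm is an inference from the design, though a safe one. The change is worth making because it alters what may be concluded and uses data that are already scheduled.

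**What to change.** 1. Make Protocol 3(e) items g and j and the SAP agree that exercise activity is analysed by both the 9-month PAAQ and the 9-month Actigraph contrasts, reported side by side in the primary activity analysis.
2. Define the Actigraph endpoint, which the documents do not yet do: the metric, what counts as a valid day, the minimum number of valid days, and the handling of insufficient wear. Report wear time by arm.
3. State when the baseline wear week falls relative to randomisation. The recruitment text places activity assessment before allocation, while item e randomises immediately after the baseline interview.
4. State that no activity benefit will be claimed on the PAAQ unless the Actigraph contrast agrees in direction.
5. Keep the PAAQ, and do not make the Actigraph the sole primary.

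The direction rule is a modest guard. With no true effect and an Actigraph contrast that is unbiased and independent of the PAAQ, agreement occurs half the time, so a 20.1% chance of a false favourable finding falls to 20.1% × 0.5 ≈ 10%. Positive correlation between the measures would make the reduction smaller. This is why the side-by-side report matters as well.

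The cost is protocol and SAP wording plus the work of defining the accelerometer endpoint; no new visit or device is needed. The downsides are some data loss from non-wear and a somewhat stricter condition for claiming an activity benefit. If outcome data have already been seen by arm, the change should be dated and reported as made after that point.

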**f) Specimen Banking for Future Uses Not Part of This Project:**

N/A

**g) Data Storage, Transmission and Confidentiality:**

Data Storage: Each subject will be assigned a unique alphanumeric identifier. The alphanumeric identifiers will be unrelated to the identity of the study subjects. All clinical data/information will be entered into a secure, online research database called REDCap only using that unique identifier. Data downloaded from REDCap and stored on MSSM computers will be encrypted and password protected, and only members of the study team will have access to the study data. All research specimens obtained will be stripped of personal identifiers (such as name, date of birth, medical record number) and will be processed/stored utilizing only the unique alphanumeric identifiers in the participating laboratories. Data abstraction forms will be completed only online. Only the research team will have access to this data. A confidential list linking subjects and their alphanumeric identifier will be recorded on a separate password protected database. This database will be located on a secure password protected desktop computer on the Division's encrypted research drive. Only the PI and the research coordinator will have access to the linking database. Databases with linked information are maintained on computers supported by the Mount Sinai server network. The research team will download deidentified data from RedCAP as needed for analysis and store all such data in password-protected files on the PI's secure study drive. MSSM policies regarding data transfer and security will be followed.

Data Access: Only authorized personnel listed on each institution's IRB will have access to the data.

Data Transfer from Recording Devices to Local Network Drive: Research interview data files from the audio/video recording devices must be transferred to each site's secure network drive within 48 hours of the interviews.

Data Transfer to Data Coordination Center (Northwestern; phase 1 only): Data will be collected separately by the NU and Mt. Sinai teams. All data will be transferred to Mt. Sinai and combined. Only de-identified study data will be transferred back to Mt. Sinai. A back-up copy of all transferred data will be maintained at Mt. Sinai. The project manager and data analyst

	Protocol Name:	Comprehensive Home-based Self-management Support for COPD Patients
	Principal Investigator:	[name], MPH
	Primary Contact Name/Contact Info:	[name]; [contact]; [contact]
	Date Revised:	4/16/21
	Study Number:	STUDY-18-01345

from our team will combine the data and maintain the master data file containing all data from each location, create a data dictionary, and be responsible for data cleaning and providing updated data to study investigators when requested.

Claims data will be requested from New York State Statewide Planning and Research Cooperative System (SPARCS) and will be managed in accordance with an executed data use agreement.

**h) Data and Safety Monitoring Plan:**

- **For projects with a Data Safety Monitoring Board/Data Safety Committee (DMSB/DMC):**

The board members will meet prior to implementation of the pilot RCT of the intervention to review the study protocol and measures to ensure that adequate protections and the plan to monitor for adverse events are adequate. They will then meet every 6 months after implementation of the pilot to review data, including the following elements: recruitment rate, study withdrawal, reasons for withdrawal, and adverse events, for a total of 3 meetings. The DSMB will specifically review: 1) hospitalization and mortality rates; 2) study disenrollment unrelated to death; 3) any patient, caregiver, and healthcare provider concerns.

**i) For other projects with greater than minimal risk a monitoring plan must be provided:**

*1. List the name(s) of the individual(s) at MSSM who will be responsible for data and safety monitoring of this study. For each individual, indicate their role, name, title, and department information. The Principal Investigator may be the only monitor of a study.*

*2. If the qualifications of an individual to serve as a monitor are not contained in the PPHS application, they must be added to the DSMP either as a narrative description or as a CV.*

**MSSM Additional Monitor (Co-I):**

Last Name: [name]  
 First Name: [name]  
 Academic Title: MA, MPH, PhD  
 Department: Division of General Internal Medicine & Geriatrics  
 Mailing Address: [REDACTED], [name]  
 [contact])  
 E-mail: [contact]

*3. Justify your choice of principal monitor in terms of the assessed risk to the research subject's health and wellbeing. In high risk studies when the principal monitor is independent of the study staff, indicate the individual's credentials, relationship to the PI, and the rationale for selection.*

The Principal Investigator is the individual who understands the benefits and risks associated with the research. The clinical experience and expertise in the field of COPD and self-management behavior interventions of the principal monitor is an adequate choice to assess the risk of research subjects' health and well-being.

*4. List the specific items that will be monitored for safety (e.g., adverse events, subject compliance with the protocol, drop outs, etc.).*

The DSMB will monitor patient safety, consider new scientific or therapeutic developments that could impact safety or trial ethics, and make recommendations to continue, terminate, or modify the trial based on interim analyses. The DSMB will specifically review: 1) hospitalization and mortality rates; 2) study disenrollment unrelated to death; 3) any patient, caregiver, and healthcare provider concerns. Adverse events that may result in subject withdrawal include disruption of previously established regular care such that the patient's health is jeopardized or excessive burden created by the time required to participate in the study.

*5. Indicate the frequency at which ACCUMULATED safety and data information (items listed in number 3 above and interim analysis of efficacy outcomes) will be reviewed by the monitor(s) or*

	Protocol Name:	Comprehensive Home-based Self-management Support for COPD Patients
	Principal Investigator:	[name], MPH
	Primary Contact Name/Contact Info:	[name]; [contact]; [contact]
	Date Revised:	4/16/21
	Study Number:	STUDY-18-01345

*the Data Monitoring Committee (DMC). Although this information must be reviewed at least annually, the higher the study risks, the more frequently reviews must be scheduled.*

Every 6 months for a total of 3 meetings

*6. Where applicable, describe rules which will guide interruption or alteration of the study design.*

The DSMB may recommend stopping the trial if there is clear evidence of harm or overwhelming benefit. Adverse events will include disruption of previously established regular care such that the patient's health is jeopardized or excessive burden created by the time required to participate in the study. The study team will monitor and report on self-reported accidents, primary care visits, participants using oxygen therapy, and unanticipated problems to the DSMB. The DSMB can recommend changes in study protocol or termination of the study if it concludes the study design causes disruptions in patient-provider continuity which jeopardized the health of the study subject or if the study imposes excessive burden on patients. Finally, the DSMB, at the request of the sponsor, will review accrual and evaluate study progress towards meeting recruitment targets.

*7. Where applicable, indicate dose selection procedures that will be used to minimize toxicity.*

N/A

*8. List any specialized grading system that will be used to evaluate adverse events (e.g., National Cancer Institute Common Toxicity Criteria).*

N/A

*9. Describe procedures that will be used to assure data accuracy and completeness.*

Additional review of data accuracy by study analyst and statistician. Aggregated data is shown to the DSMB in both closed and open meetings.

*10. Should a temporary or permanent suspension of your study occur, in addition to the PPHS, indicate to whom (NIH, FDA, sponsor, IRB) will you report the occurrence.*

Should a temporary or permanent suspension of the study occur, in addition to the PPHS, we will report this to NIH.

